**STUDY INFORMATION**

Title	Oral and Long-Acting Injectable Cabotegravir Preexposure Prophylaxis Use Among U.S. Veterans Using Veterans Health Administration Services, 2021-2025
Protocol version identifier	1.0
Date of last version of protocol	NA
EU PAS (ENCEPP) register number	TBD
Active substance	Cabotegravir
Medicinal product	Apretude
Product reference	N/A
Procedure number	N/A

Marketing authorisation holder(s)
	
ViiV Healthcare

Research question and objectives
	
 
• Objective Set 1: Estimate annual HIV diagnosis rates among Veterans in care and describe the history of PrEP use among newly diagnosed HIV patients
 
• Objective Set 2: Characterize Veterans not on PrEP but who could benefit from it and evaluate rates of HIV/STI testing and diagnoses over 12 months.
 
• Objective Set 3: 
 
- Describe demographic, clinical and sexual behavioral characteristics of Veterans initiating oral or cabotegravir long-acting (CAB LA) PrEP
 
- Estimate the proportion of CAB LA PrEP users initiating PrEP with oral lead-in (OLI) versus direct-to-injection (DTI).
 
- Describe adherence to oral PrEP and CAB LA injectable PrEP
 
- Describe patterns of PrEP use, including discontinuation, resumption, and duration of use for both oral and CAB LA PrEP.
 
- Describe HIV and STI testing, diagnoses, and antimicrobial treatment prescription for STI by PrEP modality
 
- For CAB LA PrEP users diagnosed with HIV, analyze the timing of HIV diagnoses relative to PrEP usage, injection schedules, HIV treatment, virologic suppression, STI diagnoses, and HIV drug resistance.
 
 
 

Country(-ies) of study
	
United States

Lead Author
	
PPD 

**LIST OF ABBREVIATIONS**

AE	Adverse Event
AIDS	Acquired immunodeficiency syndrome
BMI	Body Mass Index
CAB	Cabotegravir
CDC	Centers for Disease Control
CDW	Corporate Data Warehouse
CI	Confidence intervals
DTI	Direct to injection
EHR	Electronic health record
FDA	Food and Drug Administration
FTC	Emtricitabine
FU	Follow-up
GSK	GlaxoSmithKline
HBV	Hepatitis B virus
HCP	Healthcare provider
HCV	Hepatitis C virus
HIV	Human Immunodeficiency Virus
HPV	Human Papilloma Virus
HSV	Herpes Simplex Virus
IHD	Individual Human Data
IRB	Investigational Review Board
LA	Long acting
LEN	Lenacapavir
MSM	Men having Sex with Men
NA	Not applicable
OLI	Oral lead-in
PEP	Post-exposure prophylaxis
PHI	Protected health information
PrEP	Pre-exposure prophylaxis
PTSD	Post-traumatic stress disorder

**CONFIDENTIAL**

306339 Final Protocol

QPPV	Qualified Person Responsible for Pharmacovigilance
STI	Sexually transmitted infection
TAF	Tenofovir alafenamide
TDF	Tenofovir disoproxil fumarate
US	United States
VA	Veterans Affairs
VACS Index	Veterans Aging Cohort Study Index
VHA	Veterans Health Administration
ZIP	Zone Improvement Plan

**TRADEMARK INFORMATION**

Trademarks of the <<GSK\ViiV>> group of companies	Trademarks not owned by the <<GSK\ViiV>> group of companies
APRETUDE	Not applicable

## 2. SYNOPSIS

**Title:** Oral and Long-Acting Injectable Cabotegravir Preexposure Prophylaxis Use Among U.S. Veterans Using Veterans Health Administration Services, 2021-2025

### **Rationale and Background**

HIV remains a significant public health challenge in the US, with over 39,000 new diagnoses in 2023, predominantly among men, racial and ethnic minorities, and individuals aged 20–44. Pre-exposure prophylaxis (PrEP), including daily oral and long-acting injectable options, is highly effective in preventing HIV when used as recommended. However, uptake remains low, with only 36% of eligible individuals receiving PrEP in 2022. This study among individuals receiving Veterans Health Administration care seeks to generate real-world evidence on PrEP use patterns, adherence, HIV testing, STI screening, and incident HIV diagnoses among individuals using oral or injectable PrEP. The findings aim to inform strategies that optimize its effectiveness and maximize its public health impact.

### **Research Question and Objective(s)**

**Objective set 1 -Veterans in care with no evidence of HIV infection at the beginning of the calendar years under analysis**

- 1.1- Estimate the annual incidence proportion of HIV diagnoses among Veterans in care without evidence of HIV infection at the beginning of each calendar year under analysis
- 1.2- Among Veterans with an incident HIV diagnosis, characterize history of PrEP use.

**Objective set 2- Veterans in care with no evidence of HIV infection who are not on PrEP but could benefit from PrEP** (*refer to protocol section 7.2.1 for inclusion criteria*)

- 2.1- Describe the characteristics of Veterans in care who are not on PrEP but could benefit from PrEP
- 2.2- Estimate HIV testing and diagnoses rates, as well as rates of STI screening/testing rates, STI diagnoses among Veterans in care who are not on PrEP but could benefit from PrEP, over a 12-month period of follow-up

**Objective set 3- Veterans in care with no evidence of HIV infection who initiate PrEP (oral or CAB LA injectable) during the study eligibility period for PrEP initiation**

- 3.1- Describe the population of Veterans in care who initiated oral PrEP or CAB LA injectable PrEP, including their demographic and clinical characteristics, the year of PrEP initiation and the duration of follow-up
- 3.2- Describe the proportions of Veterans in care initiating CAB LA PrEP who used oral lead in (OLI) and proportion of those with direct to injection (DTI).
- 3.3- Describe adherence to oral and CAB LA injectable PrEP
  - a) Oral PrEP use only: number days oral PrEP supplied divided by number of days in the observation period
  - b) CAB LA injectable PrEP
    - Number of days covered by CAB LA PrEP divided by the number of days in the observation period
    - Timing and completion of initiation injections

- Among complete initiators with at least one maintenance injection, timing of maintenance injections: all on time, any late injection (short delay not requiring reinitiation, long delay requiring reinitiation)
  - Baseline characteristics of users with all injections on time versus users with any late maintenance injection
- 3.4- Describe patterns of PrEP use
- a) Oral PrEP:
    - Discontinuation: any discontinuation, resumption of oral PrEP
    - Duration of oral PrEP use for the first period of use
  - b) CAB LA injectable PrEP
    - Discontinuation: any discontinuation, resumption of long-acting injections (with CAB LA injectable or LEN LA injectable) or oral PrEP after discontinuation
    - Oral bridging between discontinuation of CAB LA injections and resumption of CAB LA injections
    - Duration of CAB LA PrEP use in months
      - first period of use
      - cumulative use throughout the study period in case of discontinuation followed by resumption of CAB LA PrEP injection(s)
    - Baseline characteristics of users discontinuing CAB LA PrEP versus users who did not discontinue
    - Proportion of CAB LA PrEP users with at least one maintenance injection who are on CAB LA PrEP at 12 months and 24 months after initiation and at the end of the study period
- 3.5- Described patterns of HIV and other STI testing/screening, diagnosis and STI treatment
- a) Assess the incidence of HIV testing and HIV diagnosis during the first period of PrEP use by PrEP modality
  - b) Estimate the incidence of testing for STI diagnosis and STI diagnosis by PrEP modality
    - in the 6 months preceding PrEP initiation
    - during the first period of PrEP use
  - c) Describe the proportion of diagnosed STI with a relevant antimicrobial prescription
- 3.6- Among CAB LA PrEP users diagnosed with HIV (during CAB LA PrEP use or after CAB LA PrEP discontinuation)
- a) Describe the timing of incident HIV diagnoses relative to timing of CAB LA PrEP usage and testing for HIV
  - b) Describe adherence to PrEP injection schedule, HIV treatment, virologic suppression, concomitant STI diagnosis, and HIV drug resistance

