**Data Sources**

In this study, we used data extracted from VHA's Corporate Data Warehouse (CDW), a comprehensive, continually updated repository of information from VHA's electronic health records (EHR) and administrative files. The CDW dataset includes health care encounters, laboratory tests and results, medications, diagnoses, patient demographics, and residential ZIP codes.

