Objective 1b - Among Veterans with a new HIV diagnosis during the study period	Index date	Date of HIV diagnosis
	Censoring criteria	NA
	Endpoint	PrEP use (never, use within 12 months before diagnosis, use >12 months before diagnosis)
Objective set 2 – among Veterans without evidence of HIV infection who are not on PrEP but could benefits from PrEP	Population/exposure	At least one of the following criteria: tested for or diagnosed with a bacterial STI in the past 12 months (gonorrhea, syphilis, chlamydia), tested for HIV in the past 12 months, ever had alcohol use disorder, ever used illicit non-injection drugs, ever used injectable drugs, Black women, men who have sex with men, individuals aged 18-24 years, any history of PrEP use
	Index date	First visit during the study period with criteria indicating the individual could benefit from PrEP
	Censoring criteria	Death, loss to follow-up, end of the study period, 12 months after index date, PrEP initiation, whatever comes first
	Endpoints	HIV testing, HIV diagnosis, Screening/testing for other STIs, STI diagnoses
Objective set 3 – among Veterans with a PrEP prescription	Exposure groups	Oral PrEP, CAB LA PrEP
	Index date	Start of first PrEP regimen during the study period (dispensing date for oral PrEP, injection date for CAB LA)
	Censoring criteria for calculation of proportion of days covered	Death, loss to follow-up (12 months after last clinical contact), study end, 12 months after index date whatever comes first
	Endpoints	Adherence to PrEP schedule, discontinuation and resumption of PrEP, STI screening/testing, STI diagnosis, STI treatment prescription, HIV testing and diagnosis

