## 7.2. Study Population and Setting

### 7.2.1. Inclusion criteria

- **Veterans in care without evidence of HIV infection (Obj. 1.1)- individuals will be included if they meet all of the following criteria:**

- At least one VHA health encounter in the calendar year
- $\geq 18$  years of age
- No evidence of HIV infection at the beginning of the calendar year under analysis

- **Veterans in care with a new HIV diagnosis (Obj. 1.2):**

- Incident HIV diagnosis (refer to definition in section 7.3.3)

- **Veterans in care without evidence of HIV infection who are not on PrEP but who could benefit from PrEP (Objective set 2)- individuals meeting all of the following criteria:**

- At least one VHA health encounter during the study period
- $\geq 18$  years of age
- Any of the following criteria indicating that the individual has a risk factor for HIV acquisition or a factor linked to behaviors increasing the risk of HIV acquisition and may benefit from PrEP:
  - tested for or diagnosed with a bacterial STI in the past 12 months (gonorrhea, syphilis, chlamydia),
  - tested for HIV in the past 12 months,
  - ever had alcohol use disorder,
  - ever used illicit non-injection drugs,
  - ever used injectable drugs,
  - Black women,
  - men who have sex with men,
  - individuals aged 18-24 years,
  - any history of PrEP use
- No evidence of HIV infection at the first health encounter with a criteria for PrEP

- **Veterans in care using oral PrEP only (objective set 3)**

- At least one VHA health encounter during the study period
- $\geq 18$  years of age
- Received at least one oral PrEP prescription (TDF/FTC, TAF/FTC) between January 1 2021 and 31 December 2024
- No evidence of HIV infection at the time of the first oral PrEP prescription in the study period
- Have not received a CAB LA PrEP injection between January 1, 2021, and June 30, 2025

- **Veterans in care using CAB LA for PrEP (objective set 3)**

- At least one VHA health encounter during the study period
- $\geq 18$  years of age
- Received at least one CAB LA PrEP injection between January 1, 2021 and June 30, 2025

- No evidence of HIV infection at the time of the first CAB LA PrEP injection in the study period

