##### **Veterans with a new HIV diagnosis (Objective 1a)**

PrEP use (never, ever: use within  $\leq 12$  months before diagnosis, use  $> 12$  months before diagnosis)

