### 7.3.3. Outcome definitions

#### ◆ Veterans without HIV (Objective 1)

Incident HIV diagnosis: a new HIV diagnosis is defined as either having a (1) positive screening antibody test with positive confirmatory antibody testing, (2) positive HIV viral load, or (3) documentation of HIV on the EHR problem list.

All potential HIV incident diagnosis will be subject to a detailed review for confirmation.

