##### **Veterans in care with a new HIV diagnosis (Objective 1.2)**

Among newly diagnosed people with HIV, PrEP use (never, use within  $\leq 12$  months before diagnosis, use  $> 12$  months before diagnosis) and PrEP users' characteristics will be described using counts and proportions for categorical variables and median and interquartile ranges for continuous variables.

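### Objective 1.2's closed PrEP-history classes leave recent VHA entrants without recorded PrEP nowhere to go but 'never', so prior PrEP use may be understated

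*Protocol*

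**What the plan says.** The synopsis and section 6 state the objective without classes or a look-back: "Among Veterans with an incident HIV diagnosis, characterize history of PrEP use".

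The classes are fixed in three other places:
- Table 2 in section 7.1, under Objective 1b, gives the endpoint as "PrEP use (never, use within 12 months before diagnosis, use >12 months before diagnosis".
- Section 7.3.1, where the same group is labelled Objective 1a, sets never against ever and splits ever at 12 months: "PrEP use (never, ever: use within".
- Section 7.7.1.1 repeats the three classes, with all newly diagnosed people as the denominator: "Among newly diagnosed people with HIV, PrEP use (never, use within".

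Section 7.2.1 has one entry criterion for this objective: "Incident HIV diagnosis (refer to definition in section 7.3.3". That definition, in section 7.3.3, rests on antibody tests, viral load or "documentation of HIV on the EHR problem list". It asks for no earlier negative test and no earlier time in VHA care. The parent population of Objective 1.1 needs "At least one VHA health encounter in the calendar year".

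On data, the synopsis says: "The CDW dataset includes health care encounters, laboratory tests and results, medications, diagnoses, patient demographics, and residential ZIP codes". Section 7.4 names the same source, and section 7.9 treats dispensing as the proxy for oral PrEP use.

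**The concern.** The endpoint needs at least 12 months of medication history before the diagnosis, but entry requires none. A Veteran first seen in VHA two months before diagnosis, or at the visit that produced it, can enter Objective 1.2. If no PrEP is on record, none of the three classes says that the history could not be seen.

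The share of new diagnoses without prior PrEP is a main result of this objective, and readers may take it as a measure of missed prevention. Part of it could reflect absence of data instead. The planned output would not show this. Section 7.7.1.1 describes the characteristics of PrEP users only, and the counts of visits in the previous 12 months (section 7.3.2) are specified for Objectives 2.1 and 3.1, not 1.2. Section 7.9 does not mention PrEP obtained outside VHA or before VHA entry.

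**Working it through.** **No stated figure to reproduce.** The protocol gives no expected number of diagnoses, no expected PrEP share and no share with short VHA history. Objective 1.2 is descriptive, so there is no power calculation either.

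**Reading the sections together.**
1. The classes never, within 12 months and more than 12 months leave no remainder (Table 2, 7.3.1, 7.7.1.1).
2. No minimum VHA history is required (7.2.1, 7.3.3). The diagnosis visit can itself be the one encounter needed in the calendar year. Someone not yet seen in VHA has no evidence of HIV on record at the start of that year.
3. PrEP history comes from the CDW, and no outside pharmacy or claims source is named (7.4).
4. Under 1 to 3, a recent entrant without recorded PrEP can be placed only in 'never'.

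**Direction.** Let s be the share of newly diagnosed Veterans with short VHA history. Let p1 be true ever-use in those with adequate history (taken as fully recorded) and p2 true ever-use in those with short history. Let r be the fraction of the short-history group's use that VHA records do show.

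- True ever-use = (1 − s)·p1 + s·p2
- Reported ever-use = (1 − s)·p1 + s·r·p2
- Shortfall = s·(1 − r)·p2

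The shortfall is never negative. It is zero if short-history Veterans used no PrEP (p2 = 0) or if all their use is recorded (r = 1).

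**Illustrative size.** All values of s, p1, p2 and r are assumptions.

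With p1 = p2 = p and r = 0, reported use is p·(1 − s):

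| s | p = 10% | p = 20% |
|---|---|---|
| 5% | 9.5% | 19% |
| 10% | 9% | 18% |
| 20% | 8% | 16% |
| 30% | 7% | 14% |
| 40% | 6% | 12% |

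With p1 = 10%, r = 0 and use that differs between the groups:

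| s | p2 | True | Reported |
|---|---|---|---|
| 10% | 5% | 0.9 × 10 + 0.1 × 5 = 9.5% | 9% |
| 10% | 20% | 0.9 × 10 + 0.1 × 20 = 11% | 9% |
| 30% | 5% | 0.7 × 10 + 0.3 × 5 = 8.5% | 7% |
| 30% | 20% | 0.7 × 10 + 0.3 × 20 = 13% | 7% |

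If half of the short-history group's use were recorded (r = 0.5), the last row would report 7% + 0.3 × 0.5 × 20% = 10% against a true 13%.

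**The case against.** **The coding rule is inferred.** A reader might infer that the protocol instructs analysts to code a missing VHA record as 'never'. It does not say so. The conclusion follows from a closed set of classes, a single VHA source and the absence of a look-back. A statistical analysis plan, not shown here, could add an unknown row or a minimum history. This stands as a limit on the wording. It does not remove the point, because the protocol itself fixes the classes, the entry rule and the denominator, and does not state the limitation.

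**Most histories may be long.** Section 7.4 describes a sample of patients who have accessed VA care since 2000, and section 5 dates the first oral PrEP approval to July 2012. For long-standing users the records can span the whole PrEP era. Section 5 also says that VA covers PrEP for enrolled Veterans, which lessens the need to obtain it elsewhere. This stands: the problem concerns recent entrants, and nothing shows how many there are.

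**Outside PrEP may be partly visible.** The documents do not say whether the CDW holds outside or patient-reported medications. It is therefore too strong to say that all such use is lost; it may not be captured.

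**The case review may help.** Section 7.3.3 plans a detailed review of potential incident diagnoses. It could remove some entrants whose HIV predates VHA care. Its stated purpose is to confirm the diagnosis, and nothing says that it recovers PrEP history.

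**A blunt remedy could do harm.** Setting aside every Veteran with under 12 months of VHA history as not assessable would discard recorded PrEP. One example is a Veteran first seen 6 months before diagnosis with VHA-dispensed PrEP 3 months before it. This objection is right, and the fix below avoids it.

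**Conclusion.** The point holds in a limited form. As written, the classification can place recent VHA entrants with unobservable PrEP history into 'never'. It can understate prior PrEP use by this route and cannot overstate it. Actual understatement requires that some of these Veterans used PrEP that VHA records do not show.

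A reader might infer from the illustration that prior use will be understated by 10% to 30% in relative terms. The documents do not support that. The range restates an assumed share of short-history Veterans, and it also needs equal true use in both groups and no recorded use in the short-history group. The size cannot be derived from the protocol, and long-standing VHA users are largely unaffected. The study is descriptive, so no test is at risk. What is at stake is the label and the denominator of one reported percentage, and the change is worth making because it is cheap.

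**What to change.** In Table 2, section 7.3.1 and section 7.7.1.1:
- Rename 'never' as 'no VHA-recorded PrEP'.
- Report the main PrEP-history percentages among Veterans whose first VHA encounter was at least 12 months before HIV diagnosis.
- Show Veterans with shorter history as a separate stratum. Keep any recorded PrEP in its class, and label the rest 'no VHA-recorded PrEP, history under 12 months'.
- Give full-cohort counts alongside, so that no recorded PrEP use is lost.

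In section 7.9, state that PrEP obtained outside VHA or before VHA entry may not be captured. State also that 12 months of history supports the within-12-months class but does not prove lifetime non-use. A Veteran with 13 months of history could still have used PrEP earlier without a VHA record.

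The cost is one derived date (first VHA encounter), one extra stratum and a relabelled class. The downside is a smaller denominator for the main percentages, which then describe Veterans with at least 12 months of VHA history and not all new diagnoses. The full-cohort counts are kept for that reason.

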### **Study Design**

This is a cohort study using data from the Veterans Affairs National Sample, which is composed of Veterans who receive healthcare services through the Veterans Health Administration (VHA). This national sample is representative of the Veteran population, capturing a wide range of demographic, clinical, and social characteristics.

**Population**

The study will include different cohorts:

- Veterans in care with no evidence of HIV infection at the beginning of the calendar years under analysis
- Veterans in care with no evidence of HIV infection who could benefit from PrEP but are not on PrEP (identified based on risk factors for HIV acquisition or factors linked to behaviors increasing the risk of HIV acquisition which are generally documented in Veterans health records)
- Veterans in care with no evidence of HIV infection who initiate PrEP (oral or CAB LA injectable) during the study eligibility period

**Main variables**

Exposures:

- History of PrEP use (for Veterans with a new HIV diagnosis)
- Oral PrEP and CAB LA PrEP (for Veterans initiating a PrEP regimen during the study period)

Outcomes:

- PrEP adherence and continuation patterns
- HIV testing
- Incident HIV diagnosis
- STI testing, diagnosis and treatment prescription

**Data Sources**

In this study, we used data extracted from VHA's Corporate Data Warehouse (CDW), a comprehensive, continually updated repository of information from VHA's electronic health records (EHR) and administrative files. The CDW dataset includes health care encounters, laboratory tests and results, medications, diagnoses, patient demographics, and residential ZIP codes.

**Study Size**

For the objective related to HIV incidence among Veterans, the study will leverage data from the entire eligible population of Veterans in care.

Regarding PrEP usage patterns, a feasibility assessment identified 15,477 oral PrEP users and 748 CAB LA PrEP users between January 1, 2021 and June 30, 2025.

**Data Analysis**

All analyses in this study will be descriptive, focusing on estimating frequencies of outcomes across various objectives:

**Veterans in care without HIV (Objective 1.1)**

For each calendar year, the number and percentage of new HIV diagnoses among Veterans in care will be reported.

**Veterans in care with a new HIV diagnosis (Objective 1.2)**

Among newly diagnosed individuals, PrEP usage and characteristics of PrEP users will be described using counts, proportions, medians, and interquartile ranges.

